### 5.3 Additional outcomes (not predefined in study protocol)

(S6): Change in OSAUS scores between 3 and 6 months are calculated using linear regression. Scores after 3 and 6 month will be compared by a paired t-test.

(S7) we will use a linear regression model to test associations between OSAUS score at 3 and 6 months and the following variables: experience as a GP (years), experience using POCUS (years), participation in the planned course activities (number of completed webinars and course days), number of completed pre-post quizzes, number of completed assignments, number of performed POCUS examinations.

## 6. Implementation outcomes

(PR1): The GPs keep a log-book of all scans they perform. The number of scans of the 10 modalities performed during months 1 to 3 and month 4 to 6 are summarized. Results are presented as mean(sd) or median(IQR) number of performed POCUS examinations by each GP during months 1 to 3 and during months 4 to 6. Minimum and maximum score will also be presented.

(PR2): The number of adverse events and near-miss cases associated with the use of POCUS during months 1 to 6 will be summarized for each of the ten scanning modalities. Results will be presented as total numbers and frequencies.

(PR3): We will graphically evaluate the mean OSAUS score (y-axis) at the end of the educational intervention (3 months after baseline) as a function of each of the following educational aspects (x-axis): participation in the planned course activities (number of completed webinars and course days), number of completed pre-post quizzes, number of completed assignments, number of performed POCUS examinations.

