Key secondary outcomes	
Secondary outcome 1 (S1): For GPs, participating in a POCUS training program with online support and three teaching sessions, the OSAUS scores and the item scores, after the educational period (three months after baseline), for each of the ten scanning modalities included in the curriculum.
 
Secondary outcome 2 (S2): The proportion of GPs, participating in a POCUS training program with online support and three teaching sessions, who have an ultrasound competence score (OSAUS score) of three or above after the educational period (three months after baseline), for all of the seven OSAUS items of each of the ten scanning modalities included in the curriculum.
 
Secondary outcome 3 (S3): The proportion of GPs, participating in a POCUS training program with online support and three teaching sessions, who have an ultrasound competence score (OSAUS score) of three or above six months after baseline, for each of the ten scanning modalities included in the curriculum.
 
Secondary outcome 4 (S4): The proportion of GPs, participating in a POCUS training program with online support and three teaching sessions, who rate themselves to be competent to perform un-supervised POCUS in general practice, after the educational period (three months after baseline), for each of the ten scanning modalities included in the curriculum.
 
Secondary outcome 5 (S5): The proportion of GPs, participating in a POCUS training program with online support and three teaching sessions, who rate themselves to be competent to perform un-supervised POCUS in general practice, six months after baseline, for each of the ten scanning modalities included in the curriculum.
 
Process-related outcome 1 (PR1): The number of performed POCUS examinations by each GP in the first six months after introducing POCUS use in general practice (months 1-6 after baseline).
 
Process-related outcome 2 (PR2): The number of adverse events and near-miss cases associated with the use of POCUS reported by the participating GPs in the first six months after introducing POCUS use in general practice (months 1-6 after baseline).
 
Process-related outcome 3 (PR3): The proportion of GPs, participating in a POCUS training program with online support and three teaching sessions, who have completed the different educational elements in the educational intervention three months after baseline.

3 Protocol version

Version 9. Marts 2nd 2022

4 Funding

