Secondary outcome 5 (S5): The proportion of GPs, participating in a POCUS training program with online support and three teaching sessions, who rate themselves to be competent to perform un-supervised POCUS in general practice, six months after baseline, for each of the ten scanning modalities included in the curriculum.

Implementation process related outcomes

Process-related outcome 1 (PR1): The number of performed POCUS examinations by each GP in the first six months after introducing POCUS use in general practice (months 1-6 after baseline).

Process-related outcome 2 (PR2): The number of adverse events and near-miss cases associated with the use of POCUS reported by the participating GPs in the first six months after introducing POCUS use in general practice (months 1-6 after baseline).

Process-related outcome 3 (PR3): The proportion of GPs, participating in a POCUS training program with online support and three teaching sessions, who have completed the different educational elements in the educational intervention three months after baseline.

8 Trial design

This is a hybrid effectiveness-implementation study¹⁵. We will test the effectiveness of an educational intervention in a real-world setting while gathering information on its delivery and the implementation of the intervention.

Reporting of this trial will follow STROBE guideline for reporting cohort studies¹⁶. Reporting of the protocol will follow the SPIRIT statement¹⁷. Before data collection starts, the trial will be registered on *clinicaltrials.gov*¹⁸.

Methods - Participants, interventions, and outcomes

9 Study settings

This study will be conducted in office-based general practice in Denmark with the educational sessions taking place at an ultrasound educational facility (MedSim, Central Denmark Region).

GPs in Denmark are self-employed and work in office-based general practice clinics. Denmark has a public health care system where almost all patients are listed with a GP for primary health care. Consultations and treatments are free-of-charge for patients. GPs act as gatekeepers for other primary care healthcare providers and secondary care specialists. GPs are paid through a combination of remuneration and fee-for-service financed through taxes. There is no fee for performing POCUS in primary care and GPs must cover expenses for the ultrasound device and their ultrasound education themselves.

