(S5): We calculate the proportion of GPs, who rate themselves as competent to perform POCUS un-supervised in general practice, after six months, within each of the ten scanning modalities.

Implementation process-related outcomes

(PR1): The GPs keep a log book of all scans they perform. The number of scans of the 10 modalities performed during months 1 to 3 and month 4 to 6 are summarized. Results are presented as the mean number of performed POCUS examinations by each GP during months 1 to 3 and during months 4 to 6.

(PR2): The number of adverse events and near-miss cases associated with the use of POCUS during months 1 to 6 will be summarized for each of the ten scanning modalities. Results will be presented as total numbers and frequencies.

(PR3): We will graphically evaluate the mean OSAUS score (y-axis) at the end of the educational intervention (3 months after baseline) as a function of each of the following educational aspects (x-axis).

- a. course days
- b. webinars,
- c. pre-and post-self-quizzes
- d. assignments (upload and feed-back)
- e. scans performed during the educational intervention

Background characteristics of participating GPs

At baseline the following participant characteristics will be collected: Age (years), gender (M, F, other), year of graduation from medical school, experience as a GP working in general practice (years), previous experience with ultrasound use (yes/no), previous training in ultrasound use (yes/no), scanner type (low range, mid range, high end), type of employment (practice owner/ employed/other), type of practice (collaboration, partnership, solo), location of practice (urban, rural, mixed), distance to nearest radiology department (km), number of patients assigned to the practice, number of GPs working in the practice will be presented.

13 Time schedule

Figure 7 Study timeline

Week	8	9	10	11	12	13	14	15	16	17	18	19	20	21	22	23	24	25	26	27	28	29	30	31	32	33	34	35
webinar																												
Teaching seminar																												
Skills assessment																												
Educational period																												
Transition period																												

Teaching seminars: Marts 3rd and 30th and June 9th 2022

Skills assessment: June 9th and September 1st 2022

Data collection educational period (months 1-3): Marts 3rd – June 9th 2022

Data collection after educational intervention (months 4-6): June 10th – September 1st 2022

14 Sample size

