## 2. Background of the trial

The trial is designed as a hybrid effectiveness-implementation study allowing for simultaneously evaluating the effect of a training program in real world settings and evaluating the implementation strategy (1). The trial is categorized as a type 1 hybrid design (2) with the purpose to rigorously test participants’ competences when finishing an ultrasound course and again after three months evaluate if participants maintain their competences. Secondly, we gather implementation data about the uptake of scanning procedures in practice and adherence to the training program (2).

The principal research aim is to evaluate ultrasound competences after an educational intervention by use of the OSAUS score. The study is conducted in Danish general practice and the study is registered at ClinicalTrials.gov (registration number: NCT05274581).

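### PR3 is defined as the proportion of GPs completing the educational elements but is analysed only as plots of OSAUS against participation; no calculation of the proportion is planned

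*SAP*

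**What the plan says.** The definition appears in the registration data set (Protocol section 2b) and again in the objectives (Protocol section 7). It opens "Process-related outcome 3 (PR3): The proportion of GPs, participating in a POCUS training program with online support and three teaching sessions". The numerator is then given as those GPs "who have completed the different educational elements in the educational intervention three months after baseline".

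The analysis appears in Protocol section 12: "We will graphically evaluate the mean OSAUS score (y-axis) at the end of the educational intervention", as a function of five aspects listed a to e (course days, webinars, self-quizzes, assignments, scans performed). SAP section 6 repeats the graph, "We will graphically evaluate the mean OSAUS score (y-axis"), and gives the horizontal axes as "participation in the planned course activities (number of completed webinars and course days), number of completed pre-post quizzes", followed by counts of assignments and of examinations.

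The other two process outcomes in SAP section 6 have a numerical summary. PR1 gets means or medians per GP. For PR2, "Results will be presented as total numbers and frequencies". PR3 gets only the graph.

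On purpose, SAP section 2 says "we gather implementation data about the uptake of scanning procedures in practice and adherence to the training program". On data, Protocol sections 11b and 18a and SAP section 7 all provide for recording each GP's participation during the educational period.

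**The concern.** A completion proportion and a plot of skill against participation answer different questions. The first describes adherence: of the GPs who started, how many did each part. The second describes an association among GPs who chose how much to take part, and it can look the same whether completion was high or low.

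PR1 covers uptake of scanning. PR3 is the only outcome that covers adherence to the programme. Protocol section 11b keeps GPs with low adherence in the study, so a reader needs completion figures to know how much training the P1 and P2 scores reflect. If the plan is followed as written, the outcome named in Protocol sections 2b and 7 has no planned result.

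**Working it through.** The plan states no figure for PR3, so there is none to reproduce. The check is a comparison of texts, followed by a count.

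**1. Definition against analysis**

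| | Protocol 2b and 7 | Protocol 12 and SAP 6 |
|---|---|---|
| Quantity | proportion of GPs | mean OSAUS plotted against participation |
| Numerator | GPs who completed an element | none |
| Denominator | participating GPs | none |
| Rule for completed | not given | not given |
| Needs a three-month OSAUS score | no | yes |

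**2. Is the proportion planned elsewhere?**
- SAP section 3 (Adherence) covers mentoring and reminders only.
- The baseline table in SAP section 4 has no completion variable.
- Protocol sections 11b and 18a and SAP section 7 say that participation is recorded, not how it is summarised.
- SAP section 10 names n (%) as a general format and does not link it to PR3.
- The flow chart (SAP section 10.1) covers invitations, exclusions and dropouts.
- S7 (SAP section 5.3) was a regression of OSAUS on participation and experience, so also an association. SAP section 13 drops it as adding nothing beyond PR3, which confirms that PR3 was being treated as the association analysis.

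**3. Can the plots supply the proportion?** Only in part. The SAP's axes are counts per GP. A GP at the maximum count has completed every element of that type. Below the maximum, a count does not show which elements were missed. A GP with no three-month score appears only if that score is imputed (Protocol section 20c, SAP section 10), and SAP section 10.2 restricts analysis to GPs with full data. That GP still belongs in a completion denominator.

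**4. Size.** Elements, counted from Protocol section 11a:
- seminars: 3
- webinars: introductory plus days 20, 50 and 75 = 4
- self-quizzes: pre and post for 3 seminars, 3 × 2 = 6
- assignments, numbered 1 to 13: 13
- total: 3 + 4 + 6 + 13 = 26, or 25 if the introductory webinar is not counted as an element

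Denominator: both documents expect 20 × 0.80 = 16 GPs. To show why it must be stated, assume that all 20 enrol, 16 have a three-month score, and 12 of those 16 completed an element. Among GPs with a score, completion is 12/16 = 75% (exact 95% CI 47.6% to 92.7%). Among all enrolled, it lies between 12/20 = 60% if none of the other four completed the element and (12 + 4)/20 = 80% if all did. These counts are assumptions; the documents give none.

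**5. Course days and webinars.** Protocol section 12 lists them as separate aspects. SAP section 6 puts them in one bracket, "number of completed webinars and course days". If that means a sum, its maximum is 3 + 4 = 7 (6 without the introductory webinar), and a between-seminar webinar of about 30 minutes weighs the same as a whole seminar day.

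**The case against.** The strongest reply is that nothing is lost. Participation is recorded per GP, SAP section 10 permits n (%), and with 16 to 20 GPs the horizontal axes already show much of the distribution. PR3 is the third process outcome in a single-group, descriptive study, and no other outcome depends on it.

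Most of this stands, and it limits the weight of the point. It does not remove it. The general format sentence is not tied to PR3, PR1 and PR2 do have stated summaries, and the axes show counts only for the GPs who are plotted.

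A reader might also infer more than the documents support:
- **That the proportion will never be computed.** The data allow it. What can be said is that no calculation is planned.
- **That the outcome was switched after data were seen.** The definition and the plot already stand side by side in the Protocol dated 2 March 2022. The mismatch was there from the start, and the SAP carried it forward.
- **That the SAP adds webinars to course days.** It never says so; the bracket may be shorthand for two counts. The equal-weight problem arises only if they are summed.
- **That every GP with a P1 score attended seminar 3, so that the spread on a summed axis comes mostly from webinars.** The first part holds only for observed scores, because missing ones may be imputed. The second has no supporting figure.

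**Conclusion.** The point holds. The analysis specified for PR3 does not estimate PR3 as defined, and no other part of either document plans the proportion. As written, up to 26 completion figures have no planned calculation, and the adherence aim in SAP section 2 has no planned numerical answer.

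The effect stops there: P1, P2, the secondary outcomes, PR1 and PR2 are unchanged, and the participation data are kept. The conclusion rests on reading the definition in Protocol sections 2b and 7 literally and on the absence of any other completion summary in the two documents. The ambiguity over course days and webinars is a secondary matter of clarity.

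**What to change.** - Make PR3 a table of n/N (%) for each seminar, webinar, pre- and post-self-quiz and assignment. N is all enrolled GPs, including those without a three-month OSAUS score.
- State what counts as completed for each type of element, and whether the introductory webinar is included.
- Set the data cut-off after seminar 3. The final post-self-test opens only after that seminar (Protocol section 11a), which is on 9 June, so a cut-off on that day could count a GP who takes the test the next day as a non-completer.
- Confidence intervals are optional. With 16 to 20 GPs they will be wide, and the SAP specifies none for the proportions S2 to S5.
- Keep the OSAUS plots as a separate exploratory display, and state that course days and webinars have separate axes, as in Protocol section 12.

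The cost is one descriptive table from data already recorded, plus a short entry in SAP section 13. Because the proportion is already the stated outcome, reporting it adds no new outcome, even though section 13 shows that analysis has begun.

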## 7. Data collection

### *The OSAUS score*

The participants will step-a-side to have their scanning competence assessed by a POCUS-expert assessor, who is blinded to the participants prior experience with POCUS, the number of performed POCUS examinations, and any other elements in the participants' learning process. Each POCUS-expert assessor will rate four participants twice: three months after baseline and six months after baseline. The POCUS-expert assessor will rate the individual participants screening competences by asking the below questions (blinded to the participants prior experience with POCUS, the number of performed POCUS examinations, and any other elements in the participants' learning process):

- 1) In which clinical scenarios would you perform this POCUS examination (Item 1 in the OSAUS)

The POCUS-expert assessor will then ask participants to demonstrate the POCUS examination (for maximum five minutes) to rate the following:

- 2) Applied knowledge of the ultrasound equipment (Item 2 in the OSAUS)
- 3) Image optimization (Item 3 in the OSAUS)
- 4) Systematic examination (Item 4 in the OSAUS)
- 5) Interpretation of images (Item 5 in the OSAUS)

Following the demonstration of the scan, the POCUS-expert assessor will present the participants with one picture of common pathology and ask the participants the following questions:

- 6) How would you interpret these ultrasound findings? (Item 6 in the OSAUS)
- 7) If you were to describe this examination in the medical record, what would you write? (Item 6 in the OSAUS)
- 8) What would you do if you found it? (Item 7 in the OSAUS)

### *Self-rated scanning competence*

Before the competence assessment by POCUS-expert assessor, the participants are asked to answer an online questionnaire and self-report if they have the scanning competence to perform the given POCUS examination un-supervised in general practice ((yes to a very high degree, yes to a high degree, yes to some degree, yes to a lesser degree, no, unsure).

### *Registration of performed POCUS examinations*

Participants register their POCUS use during the educational intervention (months 1-3 after baseline) and in the months following the intervention (months 4-6 after baseline) using a paper registration sheet.

Participants will bring these paper-registrations to the teaching seminars and the final OSAUS assessment, where the principal investigator will collect the data from each participant.

### *Adverse events and near-miss cases*

Adverse events (AE) and serious adverse events (SAE) related to or possibly related to the use of POCUS will be registered during all time after the training sessions.

At the teaching sessions, participating GPs will be taught how to report AE and SAE related or possibly related to the use of POCUS as well as near-miss cases. These events will be reported to the study adverse event committee in an online questionnaire specifically designed for this purpose. The participants will have a link for an online questionnaire in SurveyXact (Rambøll, Aarhus Denmark) where they will register: (1) Type of POCUS, (2) indication for the examination, (3) description of the event, (4) participant's reflections after the events and (5) questions for the adverse events committee.

The reporting of AE/SAEs to the study adverse event committee does not substitute or have any influence on the GPs responsibility to report adverse events to the Danish authorities (UTH anmeldelse). Such reporting will not be collected in this study.

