5d Composition, roles, and responsibilities of the steering committee and safety committee (see Item 21a for data monitoring committee)

A steering committee affiliated with CAM AAU (TL, UM, TMJ, SKA, MBJ and CAA) will handle and oversee the development of the intervention, the coordination and organisation of the ultrasound courses, and the data collection and data management.

A safety committee will be set up to handle all reports of adverse and suspected adverse events (AEs) and serious adverse events (SAEs). MBJ will head the committee.

Introduction

6 Background and rationale

The interest in performing point-of-care ultrasound (POCUS) in general practice is increasing, advanced due to the development of affordable, mobile ultrasound scanners. Furthermore, primary care residents are commonly exposed to POCUS during their hospital-based training laying the foundation for its later use in an office-based setting.

Ultrasound is a highly user-dependent image modality which requires the ability to integrate anatomy, image acquisition, and clinical knowledge². A robust training program in the use of POCUS is mandatory to minimize adverse effects in the form of false positive and false negative results^{3 4}.

An increasing body of evidence shows that GPs can perform POCUS in a safe manner^{5 6}.

However, GPs are faced with unique educational challenges⁷. While hospital-based physicians have the advantage of consulting with their peers if they experience problems with interpreting difficult cases, GPs work alone without easy access to more experienced colleagues.

Furthermore, GPs face a wide variety of clinical conditions which require the GP to be able to perform multiple scanning modalities some of which may be infrequently used⁸. This may lead to a decay in competency. Therefore, measures must be put in place to maintain the retention of POCUS skills after initial POCUS training. While there are multiple studies showing that GPs can learn different scanning modalities, evidence is more limited as to their ability to keep competencies over time³.

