After the first teaching seminar participants are encouraged to start practicing POCUS examinations. This phase in the learning process is considered and articulated as a training phase, where participants are to conduct as many POCUS examinations as possible with a primary aim of training without having to draw conclusions based on their scans. As such, participants are in this phase encouraged to treat patients as usual without taking scan results into account.

Participants are also encouraged to train examinations on volunteers e.g. family members, as the goal in this phase is to perform as many examinations as possible.

During the three weeks between the two teaching seminars, participants are encouraged to register all POCUS examinations in their individual logbook and note reflections and questions that occur during this process. It is recommended that participants aim to perform a minimum of three POCUS examinations of each scanning modality in the curriculum and upload one POCUS examination of each scanning modality for review by the teachers (assignments 2, 3, 4, 5, and 6). Midway in the practice phase (day 20), participants will be invited to participate in a half-an-hour webinar. In this webinar, one of the teachers will go through some of the encountered problems and difficulties uploaded or posted on the online platform. Participants will also have the opportunity to ask questions.

Prior to the second teaching seminar, assignment 7 is sent to the participants. In this assignment participants have to register their specific focus points and individual learning goals for the second seminar as well as any questions they may have to the teachers.

A specific pre-self-quiz will be available before teaching seminar 2. This self-test will access basic knowledge of the five POCUS scans introduced at the first teaching seminar and prime the participants for the learning objective of the second teaching seminar.

Teaching seminar 2

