This phase in the learning process is considered and articulated as a developing phase, where participants continue to develop their scanning skills and routines. The participants are encouraged to use POCUS examinations on all patients with relevant clinical conditions suited for POCUS and to work with the integration of POCUS into their clinical practice and medical decision making. It is important in this phase that the participants develop routines and become comfortable performing POCUS examinations. During the eight weeks between the teaching seminars 2 and 3, participants are encouraged to register all POCUS examinations in their individual logbook in the online platform and note reflections and questions that occur during this process. The participants will still have the opportunity to consult the teachers during this phase by uploading questions, images or videos to the online platform. It is again recommended that participants perform a minimum of three POCUS examinations on patients within each scanning modalities during the eight weeks and that participants upload at least one POCUS examination of each of the five new scanning modalities for review and feed-back (assignments 8-12).

During the eight weeks, participants will be invited to participate in two half-an-hour webinars (on day 50 and 75). At these webinars, one of the teachers will go through some of the encountered problems and difficulties uploaded or posted on the online platform and present images and videos of common pathologies with the 10 selected POCUS modalities. Participants will also have the opportunity to ask questions and the teacher will have an ultrasound device and a volunteer available for live POCUS demonstration.

Before the third and final teaching seminar, the participants will be asked to complete a pre-self-quiz and to send in a list of questions or topics that they want included in the final teaching seminar (assignment 13).

[figure not shown]
Teaching seminar 3

Before the final teaching seminar, the teachers will prepare feedback for each participant based on the information gathered about each participant, i.e., from notes in the logbook, the uploaded scans, impressions from teaching seminars, the correspondence in the chat function, etc.

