During the study, the principal investigator is available for consultation for the participating GPs in order to resolve any problems or obstacles. Monthly reminders will be sent to the participating GPs remaining them to include patients and contact the research team in case of problems.

19 Data management

The OSAUS assessment will be filled out by the expert assessors in questionnaires using tablets. The expert assessors will access the SurveyXact app (Rambøll, Aarhus, Denmark) on the tablets using unique access links. The Raters will then insert the GP ID number and fill out the questionnaire. After filling out the questionnaire, the access will close. As internet access may be unstable at the training facilities, the questionnaire can be filled out on both offline and online tablets. If the tablet is online, the questionnaire is stored directly on SurveyXact's server. If the tablet is offline, the questionnaire is stored safely in the app for direct upload when internet access is achieved. Questionnaires stored in the app cannot be accessed. The questionnaires stored on SurveyXact's server can only be accessed by the research team. Backup copies from the SurveyXact server are weekly collected and stored at a secure server at Aalborg University during the data collection period.

The participating GPs will be asked to bring paper versions of the registration sheets (Logbook) at the third training day and the final day of skills assessment, where the principal investigator will collect these and bring them to CAM AAU, where the questionnaires will be imputed into the database by a research assistant.

All study data registered on the online platform will be transferred and imputed in an excel sheet at the end of the educational intervention. All digital study related data are stored on secure server on Aalborg University and handled according to the General Data Protection Regulation.

20a Statistical methods for analysing primary and secondary outcomes.

All statistical analyses will be performed using STATA version 17 (StataCorp, Texas, USA) and analyzed according to a predefined statistical analysis plan, which will be uploaded prior to the data collection for the primary outcome (three months after baseline).

20b Methods for any additional analyses (e.g. subgroup and adjusted analyses).

Sensitivity analyses will be performed without imputation of missing values by only including complete OSAUS scores.

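### PR2 rests on self-report by the scanning GP, with no event question and no nil return, so a low count cannot separate few events from few reports

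*SAP*

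**What the plan says.** PR2 is one of three implementation outcomes and the only outcome in either document that concerns harm. Protocol section 7 defines it as "The number of adverse events and near-miss cases associated with the use of POCUS reported by the participating GPs in the first six months" after POCUS is introduced. SAP section 6 says "The number of adverse events and near-miss cases associated with the use of POCUS during months 1 to 6 will be summarized" by modality, as totals and frequencies, and names no denominator.

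The route in is the same in Protocol section 18a and SAP section 7. GPs are taught how to report, near-misses included, and complete a dedicated online form that goes to the adverse event committee. Protocol section 22 makes reporting of SUSARs, SAEs and AEs an obligation. Near-misses, which PR2 also counts, are not in that list.

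Other contacts and sources:
- Protocol section 11c and SAP section 3 describe reminders to register scans.
- Protocol section 18b says "Monthly reminders will be sent to the participating GPs remaining them to include patients and contact the research team in case of problems".
- On reports to the Danish authorities, SAP section 7 says "Such reporting will not be collected in this study".
- In Protocol section 11a, GPs are recommended to "upload one POCUS examination of each scanning modality for review by the teachers" between seminars 1 and 2, and to "upload at least one POCUS examination of each of the five new scanning modalities for review and feed-back" between seminars 2 and 3. No text sends an error seen there to the committee.

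**The concern.** Protocol section 6 says that robust training "is mandatory to minimize adverse effects in the form of false positive and false negative results". Errors of that kind are often not apparent to the person who made them. For an event to enter PR2, the scanning GP must recognise it, judge it possibly related to the scan, and open the form unprompted. A gap at any of these steps lowers the count, and the data carry no trace of it.

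Two things depend on this count. The main paper will show PR2 for ten modalities, and neither document plans a statement on how complete the reporting was. The safety committee, which under SAP section 9 can end the trial, works from the same stream of reports.

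**Working it through.** **1. The plan's own figures.** Protocol section 14 and SAP section 8 expect 20 × 0.80 = 16 GPs and 16 × 10 = 160 OSAUS questionnaires. Both reproduce. For PR2 the documents give no expected rate, reporting completeness or precision, so there is no PR2 figure to reproduce.

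**2. What each route can deliver.**

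| Route | Source | Yields an event? | Yields an explicit 'none'? |
|---|---|---|---|
| Online event form | Protocol 18a, SAP 7 | Yes, if the GP starts it | No |
| Scan-registration reminders | Protocol 11c, SAP 3 | Not asked | No |
| Monthly reminder | Protocol 18b | Only if the GP raises a problem | No |
| Log collection, three and six months | Protocol 19, SAP 7 | Not asked | No |
| Teacher review of uploads | Protocol 11a | No route stated | No |

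No row fills the last column, so a count of zero has two explanations that the data cannot separate.

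**3. How much that can matter (illustration).** Inputs from Protocol section 11a are the recommended minimums: 3 scans for each of the 5 modalities taught by then (practice phase), and 3 patient scans for each of 10 modalities (developing phase).
- Both phases: N = 16 × (3×5 + 3×10) = 16 × 45 = 720.
- Developing phase only: N = 16 × 30 = 480.

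Let p be the true event rate per scan and s the share of events reported. The documents give neither, so both are assumed. Then P(zero reported) = (1 − p·s)^N. Setting this to 0.05 gives the one-sided upper 95% bound p = (1 − 0.05^(1/N)) / s.

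| s | Bound, N = 720 | Bound, N = 480 | P(zero reported) at p = 1%, N = 720 |
|---|---|---|---|
| 100% | 0.42% | 0.62% | 0.001 |
| 50% | 0.83% | 1.24% | 0.027 |
| 25% | 1.66% | 2.49% | 0.165 |
| 10% | 4.15% | 6.22% | 0.487 |
| 5% | 8.30% | 12.44% | 0.698 |

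A true rate of 1% means 720 × 0.01 = 7.2 expected events. Zero reports would then be very unlikely under full reporting, but close to an even chance if one event in ten is reported.

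**4. Clustering.** Scans are nested in GPs. With 45 scans per GP and an assumed intraclass correlation of 0.01, the design effect is 1 + 44 × 0.01 = 1.44, the effective N is 720/1.44 = 500, and the full-reporting bound rises to 0.60%. With 0.05 it is 3.2, 225 and 1.32%.

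**5. Reach of the uploads.** The recommended uploads come to 16 × (5 + 5) = 160, or 160/720 = 22% of the minimum scans, all in months 1 to 3 of a six-month outcome.

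**The case against.** The strongest reply is that PR2 is an openly labelled process outcome. Protocol section 7 says in its definition that the events are those GPs report. Reporting is obligatory, GPs are trained in it, the form is dedicated, and the monthly message invites contact about problems. All of this stands. It would be wrong to infer that reporting is voluntary, or that the plan will present a low count as proof of safety, since neither document says so.

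A reader might also infer that the study ignores error sources it already holds. That goes too far:
- Authority reports are not held by the study. They come from the same GPs, so an error the GP does not recognise is in neither channel.
- Reminders are outgoing messages, not an error source.
- Uploads are held, but those recommended fall in months 1 to 3. In the practice phase they may show volunteers, and GPs are told then not to act on results. A misread image need not be an adverse event.
- The assignments are not the only second look. Item 8 of the platform list in Protocol section 11a also lets GPs send images to teachers by chat.
- The registration sheet (Protocol Figure 9, poorly legible) appears to have a column for the consequence of the scan, but no text links it to PR2.

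A further temptation is to convert Table 1 into missed harm. Nine modalities have accuracy figures (knee read as 84% and 93%), with 16 × 3 = 48 scans each and 432 in all. The sums of (1 − specificity) and (1 − sensitivity) are 0.796 and 1.103. Wrong results are 48(1 − prevalence) × 0.796 + 48 × prevalence × 1.103, which is 38.9 at 5% prevalence and 45.6 at 50%. The arithmetic is right, but it counts wrong scan results under one assumed prevalence for all modalities. It does not count adverse events or near-misses and does not measure under-reporting of PR2.

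What the reply does not answer is that an obligation cannot produce a report of an unrecognised error, and that without a nil return nobody can tell whether the obligation was met.

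**Conclusion.** The point holds as a limit on interpretation that is cheap to reduce. It is not a contradiction in the plan. PR2 depends on unprompted self-report by the scanning GP, and the design does not let a low count distinguish few events from few reports.

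On the 720-scan illustration, the rate compatible with zero reports runs from 0.42% to 8.30% as assumed completeness falls from 100% to 5%, a factor of 20. This assumes 16 GPs, the recommended minimum scans and independent scans. Actual numbers are unknown, months 4 to 6 have no stated minimum, and clustering would widen every bound. The main conclusion rests on none of these figures. It follows from the absence of an event question and a nil return.

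**What to change.** 1. Add one mandatory yes/no item, such as *any adverse event or near-miss from a scan since last contact?*, to the monthly reminder and to the log collection at three and six months. A yes leads to the existing form.
2. Report how many GPs gave an explicit no, and how many did not answer.
3. Label PR2 *GP-reported events*, show it per modality against logged scans (the PR1 data), and state that ascertainment is incomplete.
4. Optionally, let teachers use the same form to flag a misread patient scan seen in an upload. Show these as a separate category and do not add them to PR2. This needs a short case definition and a check for duplicates.

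Cost: about six monthly items and two at log collection for each of 16 GPs, so 16 × 8 = 128 one-item answers, with no new visits. The downside is a possibly higher event count and slightly more work for GPs.

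SAP section 13 records a decision taken during data analysis, so collection has probably closed. In that case only step 3 still applies.
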